3.5. Study Group

Data from all sites will be summarized together. Patients will be grouped into the following 3 study groups:

- 1) 004 Placebo: patients in Study 006 who previously received placebo in Study 004.
- 2) 004 Patisiran: patients in Study 006 who previously received patisiran in Study 004.
- 3) 003 Patisiran: patients in Study 006 who previously received patisiran in Study 003.

Summary tables and figures will include presentations by study group and overall.

3.6. Adjustments for Covariates

No formal statistical analyses that adjust for possible covariate effects are planned.

3.7. Multiple Comparisons/Multiplicity

Multiplicity is not of concern for this study with a descriptive interpretation.

3.8. Subpopulations

No analyses of patient subgroups are planned.

3.9. Withdrawals, Dropouts, and Loss to Follow-up

Patients are free to withdraw from the study at any time and for any reason, without penalty to their continuing medical care. Every effort should be made to complete the Early Withdrawal (EW) visit, if applicable. Patients who permanently discontinue treatment are to be withdrawn from the study.

In the event a patient withdraws early from the study, the contract research organization (CRO) Medical Monitor must be informed immediately. If an AE is the reason for withdrawal, the patient will remain under the supervision of the Investigator for protocol-specified safety follow up procedures.

When a patient withdraws from the study, the primary reason for withdrawal must be recorded in the appropriate section of the electronic case report form (eCRF) and all efforts will be made to complete and report the observations as thoroughly as possible.

3.10. Missing Data

3.10.1. Partially Missing Efficacy Endpoints

Specific algorithms will be used to impute values and/or subcomponents of particular assessments when subcomponents are missing (mNIS+7, NIS+7, Norfolk QOL-DN, EQ-5D-5L, R-ODS, and COMPASS-31; see Section 7.1, Section 7.2, Section 7.3, Section 7.4, and Section 7.5). The result of the partial imputation (either a non-missing or missing value) will be used in all statistical analyses.

In general, there will be no imputation for missing data for other efficacy endpoints unless specified otherwise. All data recorded on the eCRF will be included in data listings that will accompany the CSR.

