4.5. Efficacy Analyses

Efficacy analyses will be based on the full analysis set. Summaries will be provided for each scheduled time point by study group and overall.

Neurologic impairment will be assessed by mNIS+7, NIS+7, and NIS. The observed values and changes from baseline in the composite and component scores of mNIS+7, NIS+7, and NIS will be summarized. The mNIS+7 composite score consists of the NIS weakness (NIS-W) and reflex (NIS-R) domains, quantitative sensory testing (QST) by body surface area including touch pressure (TP) and heat pain (HP), 5 nerve conduction studies ($\Sigma 5$ NCS), as well as autonomic assessment through postural blood pressure (PBP). The NIS+7 includes the NIS-W, NIS-R, NIS sensation (NIS-S), and $\Sigma 7$ Nerve tests (including sum of 5 NCS which overlaps but is not identical to the $\Sigma 5$ NCS calculated for mNIS+7 above, vibration detection threshold (VDT), and heart rate response to deep breathing [HRdb]). The total NIS score is the sum of NIS-W, NIS-R, and NIS-S. Scoring algorithms for mNIS+7, NIS+7, and NIS, including methods for handling missing components, are included in Section 7.1.

Patient reported QOL will be assessed by the Norfolk QOL-DN total score (Study 003 patients do not have to complete this assessment) and by the EQ-5D-5L index value (using U.S. references to calculate the index). Overall health will be assessed by the EQ-VAS and disability will be assessed by the R-ODS. Patient reported autonomic neuropathy symptoms will be assessed by the COMPASS-31 total score. The observed values and changes from baseline in these measures will be summarized. Continuous summaries of each Norfolk QOL-DN and COMPASS-31 domain score, as well as categorical summaries of each EQ-5D-5L domain will also be provided. Scoring algorithms for the Norfolk QOL-DN, EQ-5D-5L, R-ODS, and COMPASS-31 are included in Section 7.2, Section 7.3, Section 7.4, and Section 7.5.

Motor function assessments will include a timed 10-meter walk test and test of grip strength in the dominant arm, as well as an evaluation of ambulation using PND score and FAP stage. The observed values and changes from baseline in 10-meter walk test speed and grip strength will be summarized. Categorical summaries of FAP stage and PND score will also be provided.

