7.1.1.1. Modified Neuropathy Impairment Score + 7 (mNIS+7)

There are 5 components within mNIS+7 total score including NIS-W, NIS-R, QST, $\Sigma 5$ NC, and postural BP, as described in detail below.

1. NIS-W is the sum of the cranial nerve components (3rd nerve, 6th nerve, facial weakness, palate weakness, tongue weakness) and muscle weakness components (respiratory, neck flexion, shoulder abduction, elbow flexion, brachioradialis, elbow extension, wrist flexion, wrist extension, finger flexion, finger spread, thumb abduction, hip flexion, hip extension, knee flexion, knee extension, ankle dorsiflexors, ankle plantar flexors, toe extensors, toe flexors). Assessments are performed separately for the right- and left-hand side of the body. Scoring for each component is 0 (normal), 1 (25% weak), 2 (50% weak), 3 (75% weak), 3.25 (move against gravity), 3.5 (movement, gravity eliminated), 3.75 (muscle flicker, no movement), and 4 (paralysis). The maximum total score for NIS-W is 192.
2. NIS-R is the sum of the reflex components (biceps brachii, triceps brachii, brachioradialis, quadriceps femoris, and triceps surae). Assessments are performed separately for the right and left foot. Scoring for each component is 0 (normal), 1 (decreased) and 2 (absent). Adjustments are made for the age of the patient (e.g., absent reflexes in a patient older than 60 is assessed as 0, or normal). The maximum total score for NIS-R is 20.
3. QST measures HP and TP from among 10 distributed anatomical sites on one side of the body. Scoring is based on point abnormality (<95th = 0 point, $\geq 95^{\text{th}} - < 99^{\text{th}}$ = 1 point and $\geq 99^{\text{th}}$ = 2 points). The test score is 2 times the total scores for QST of HP by body surface area (QST-BSA_{HP}) and QST of TP by body surface area (QST-BSA_{TP}). The maximum total score for QST is 80. Missing values for QST-BSA_{HP} and QST-BSA_{TP} will be imputed separately (see below), but only the total score will be summarized.

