4. $\Sigma 5$ nerve conductions include ulnar CMAP, ulnar SNAP, sural SNAP, tibial CMAP, and peroneal CMAP. Their measured values were transformed to normal deviates from percentile values correcting for applicable variables of age, gender, height or weight as based on earlier studies of a large healthy patient reference cohort. Additionally, these percentile values were expressed as points from obtained percentile values (i.e., $> 5^{\text{th}}$ = 0 points; $\leq 5^{\text{th}} - > 1^{\text{st}}$ = 1 point and $\leq 1^{\text{st}}$ = 2 points (and similarly when abnormality is in the upper tail of the normal distribution). The total score is calculated as the mean point scores of the non-missing 5 nerve tests and multiply this value by 5. The maximum total score for $\Sigma 5$ NC is 10.
5. Postural BP test measures autonomic function to address risk of orthostasis. The points are assigned based on change in PBP (> -20 mmHg = 0 points; $> -30 - \leq -20$ mmHg = 1 point; and ≤ -30 mmHg = 2 points).

If at least 1 value at a time point and (replicate) assessment is missing then do the following:

- Missing items within the $\Sigma 5$ NCs component (e.g., missing tibial CMAP) are handled in Step 4 above.

- If 1 of the following components or subcomponents of mNIS+7 (NIS-W, NIS-S, QST-BSA_{TP}, QST-BSA_{HP}, the entire $\sum 5$ NCs, or postural BP) is missing from 1 of the assessments at a time point (“replicate A”), then impute via substituting the component from the other assessment at that time point (“replicate B”) → recover 2 complete replicate mNIS+7 measures A and B at that particular time point.
- If both replicates A and B are incomplete at different components, insert replicate A components into replicate B and replicate B components into replicate A as necessary → allow recovery of 2 complete replicate mNIS+7 measures A and B.
- If NIS-W component is missing from both replicates A & B, mNIS+7 score is considered as missing. If 1 of the other mNIS+7 components or subcomponents (NIS-R, the entire $\sum 5$ NCs, QST-BSA_{TP}, QST-BSA_{HP}, or postural BP) is missing from both replicates A and B, impute this component as the average of the component using data from any of the patients who had non-missing data for that component at the time point.
- If 1 entire mNIS+7 replicate is missing, do not impute the missing replicate; just use the singular (other) replicate rather than the average of the 2 in subsequent calculations.

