- If no single complete mNIS+7 measure can be found or recovered, mNIS+7 score is considered as missing.

In 006, if the last mNIS+7 assessment in the parent study was done more than 45 days before the first dose in 006, mNIS+7 will be reassessed on Day 1 in 006. It is expected that very few patients will have this Day 1 assessment; therefore, the imputation algorithm for missing components in mNIS+7 will be slightly different from the general algorithm. If NIS-W is missing from both replicates, the mNIS+7 total score will be considered as missing, similar to the general algorithm. If any other component is missing from both replicates, the component score will be imputed by last observation carried forward (LOCF) using the imputed average component score from the last assessment in the parent study.

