7.1.2. Neuropathy Impairment Score + 7 (NIS+7)

The components of NIS+7 include the following:

1. NIS-W as described in previous section.
2. NIS-R as described in previous section.
3. NIS-S is the sum of the finger and toe sensation components (TP, pin-prick, vibration, joint position). Assessments are performed separately for the right- and left-hand side of the body. Scoring for the sensory assessment is 0 (normal), 1 (decreased) and 2 (absent). The maximum total score for NIS-S is 32.
4. $\sum 7$ nerve tests normal deviates include the following:
 - $\sum 5$ nerve conductions:
 - For peroneal DL and tibial DL, using normal deviate.
 - For peroneal CMAP, peroneal CV and sural SNAP, using $(-1) \times$ normal deviate.
 - Vibration detection threshold (VDT): using normal deviate.
 - Heart rate response to deep breathing (HRdb): using $(-1) \times$ normal deviate.

Each normal deviate ranges from -3.72 to +3.72. The total score is calculated as the mean normal deviates of the non-missing 7 nerve tests multiplied by 7. The total score ranges from -26 to +26.

Missing values will be handled as follows:

- Missing items within the 7 nerve tests are handled in Step 4 above.
- If a component of NIS+7 (NIS-W, NIS-R, NIS-S, and 7 nerve tests) is missing from replicate A, then impute the component from replicate B → recover 2 complete replicate NIS+7 measures A and B.
- If both replicates A and B are incomplete at *different* components, insert A components into B and B components into A as necessary → recover 2 complete replicate NIS+7 measures A and B.
- If NIS-W component is missing from both replicates A & B, NIS+7 score is considered as missing. If 1 of the other NIS+7 components (NIS-R, NIS-S, and 7 nerve tests) is missing from both replicates A and B, impute this component as the average of the other patients at this time point who had non-missing data.
- If 1 entire NIS+7 replicate is missing, use the singular (other) replicate rather than the average of the 2 in subsequent calculations.
- If no single complete NIS+7 measure can be found or recovered, NIS+7 score is considered as missing.

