7.1.3. NIS Total Score

NIS total score is the sum of NIS-W, NIS-R, and NIS-S. The handling of missing data is similar as the steps described for mNIS+7. If NIS-W is missing from both replicates, NIS score is considered as missing.

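### The SAP does not confine cross-patient average fills to the composite scores, so component tables for mNIS+7, NIS+7 and NIS can report unmeasured values as observed

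*SAP*

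**What the plan says.** - **Scope of the imputed result, SAP Section 3.10.1.** After listing mNIS+7 and NIS+7 among the assessments with their own algorithms, the section says: "The result of the partial imputation (either a non-missing or missing value) will be used in all statistical analyses".
- **Tables planned, Section 4.5.** "The observed values and changes from baseline in the composite and component scores of mNIS+7, NIS+7, and NIS will be summarized".
- **Fill rule for mNIS+7, Section 7.1.1.1.** For a component or subcomponent other than NIS-W that is missing from both replicates, the instruction is to "impute this component as the average of the component using data from any of the patients who had non-missing data" at that time point.
- **Fill rule for NIS+7, Section 7.1.2.** For NIS-R, NIS-S or the 7 nerve tests: "impute this component as the average of the other patients at this time point who had non-missing data".
- **NIS total, Section 7.1.3.** "The handling of missing data is similar as the steps described for mNIS+7".
- **QST, Section 7.1.1.1.** Missing heat-pain and touch-pressure scores "will be imputed separately (see below), but only the total score will be summarized".
- **Exception for weakness, Section 7.1.1.1.** "If NIS-W component is missing from both replicates A & B, mNIS+7 score is considered as missing". Sections 7.1.2 and 7.1.3 have the same exception.
- **Day 1 reassessment, Section 7.1.1.1.** A component missing from both replicates is carried forward, "using the imputed average component score from the last assessment in the parent study".

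Section 3.2 makes n, mean, median, SD, minimum and maximum the statistics shown, and Section 3.5 presents them for three study groups and overall.

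**The concern.** Filling a component has one legitimate purpose here: a patient whose other components were measured can still contribute a composite. In the component's own table there is nothing to rescue. The filled value carries no information about that patient, yet it adds one to n and supplies a change that the patient did not have.

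Component tables are read to see which part of the composite moves on long-term treatment. The rows open to this are NIS-R, NIS-S, QST, the nerve tests and postural blood pressure. The study is purely descriptive, so n, mean and SD are its results. No test or power calculation is at stake.

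Neither fill rule limits the average to the patient's own study group, while the tables are split by group. A fill therefore also pulls group means toward the all-patient value.

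**Working it through.** **Inputs.** The SAP states no sample size from a power calculation, no missing rate and no within-patient correlation, so there is no planned figure to reproduce. Assumed: N = 200 patients at a visit; filled share f = 5%, 10% or 20%; baseline-to-visit correlation ρ = 0.5, 0.8 or 0.9, with equal SDs at the two times. Let k be the number filled and m = N − k the number measured.

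**1. n and visit SD, overall column.** The table shows N instead of m. A value filled with the measured mean adds nothing to the sum of squares, while the divisor grows from m − 1 to N − 1. The SD is therefore multiplied by √[(m − 1)/(N − 1)].

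| Filled | m | n overstated (N/m − 1) | SD multiplier |
|---|---|---|---|
| 5% | 190 | 5.3% | √(189/199) = 0.975 |
| 10% | 180 | 11.1% | √(179/199) = 0.948 |
| 20% | 160 | 25.0% | √(159/199) = 0.894 |

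The overall visit mean equals the measured mean whatever the share filled.

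**2. Study-group rows.** Let D be the all-patient mean minus the measured group mean. The group's visit mean shifts by f × D; for example, 10% filled and a 10-point gap give 0.10 × 10 = 1.0 point. The group variance becomes [(m − 1)s² + (km/N)D²]/(N − 1), with N, k and m now counted within the group. This is below s² as long as D² < s²N/m. The group SD is therefore understated unless the gap is about one SD or more.

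**3. SD of change, missing at random.** In units of the common SD, a measured change has variance 2(1 − ρ). A filled change is a constant minus the patient's own baseline and has variance 1. The ratio to the correct SD is √{[(1 − f)·2(1 − ρ) + f] / [2(1 − ρ)]}.

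- ρ = 0.9, f = 10%: √[(0.18 + 0.10)/0.20] = 1.18. At 5% and 20% the ratio is 1.10 and 1.34.
- ρ = 0.8: 1.04, 1.07 and 1.14 at 5%, 10% and 20%.
- ρ = 0.5: 1.00 at every share.

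A simulation (400 runs, N = 200) agrees to within 0.01. The SD of change can therefore rise while the visit SD falls.

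**4. Mean change when the gaps fall on sicker patients.** Suppose the true mean change is 0, ρ = 0.9, and all filled patients have a baseline more than 0.5 SD worse than average. Their mean baseline is 0.3521/0.3085 = 1.141 SD. At f = 10% the measured patients have a mean baseline of −0.10 × 1.141/0.90 = −0.127 and a mean visit value of 0.9 × (−0.127) = −0.114.

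- Filled table: baseline 0, visit −0.114, so a mean change of −0.114 SD. Higher scores are worse, so this looks like improvement.
- Measured patients only: −0.114 + 0.127 = +0.013 SD.

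At 5% and 20% the simulated filled changes are −0.053 and −0.257 SD, against +0.007 and +0.029 SD for measured patients only. The scenario is demanding: only 30.9% of a normal population lies above 0.5 SD, so 20% filled means 0.20/0.309 = 65% of those patients lack the component in both replicates.

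**The case against.** **Section 3.10.1 may mean only the final score.** Its heading concerns endpoints, and the algorithms in Section 7.1 aim at recovering complete composites. On that reading no filled component enters its own table. The reading is possible, and the SAP never says expressly that a filled component is tabulated. Two places point the other way. The QST sentence has a component score (maximum 80) summarised after its parts are imputed, and the Day 1 rule treats an imputed component score as a stored value. If both readings survive, two programmers can produce different n, SD and mean change from the same plan.

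**QST is a mixed case.** The fill is worded for one missing component or subcomponent, so a QST total with one part filled still contains a measured part. This stands, and the plan needs to say whether such a total counts as measured.

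**Much of the score is protected.** NIS-W is never average-filled. It carries 192 of 304 mNIS+7 points, 192 of 270 NIS+7 points and 192 of 244 NIS points (192 + 20 + 32). A component missing from one replicate takes the patient's own other replicate, single missing nerve tests are handled from that patient's remaining tests, and a Day 1 gap is carried forward from that patient's parent-study assessment. All of this stands and limits the point to components absent from both replicates.

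**Keeping one patient set lets component changes add up to the composite change.** That is a real advantage of filling, and the fix gives it up.

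**A reader might infer that the component tables are wrong as they stand.** The documents do not support that. The rate of double-replicate gaps is not given; if there are none, the tables are right. A false improvement needs missingness related to severity, and inflation of the SD of change needs a correlation above 0.5. Neither is documented.

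**Conclusion.** The point holds as a gap in the rules. As written, Sections 3.10.1, 4.5 and 7.1.1.1 to 7.1.3 let components other than NIS-W, when filled from other patients' data, appear in component tables as observed. Where that happens, n is overstated, the visit SD is understated (within a study group, unless the group's mean lies about one SD or more from the all-patient mean), and mean change can be biased in either the overall or the group columns.

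The size rests on the assumed filled share: 5%, 10% and 20% give n too high by 5%, 11% and 25% and a visit SD too low by about 2.5%, 5% and 11%. The figures for change rest in addition on assumed correlations and, for the mean, on selective missingness. They show what could happen and do not estimate what will. The composite scores are outside this point. It is worth correcting because the remedy is cheap and these summaries are the study's output.

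**What to change.** Amend Sections 3.10.1 and 4.5 along these lines:

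- A component filled with a cross-patient average is used only to compute the composite.
- Summaries of component values include patients with that component measured in at least one replicate at that visit.
- Summaries of component change include patients with that component measured in at least one replicate at both baseline and the visit. A measured visit value without a baseline thus stays in the table of values.
- QST counts as measured only if both touch pressure and heat pain were measured.
- A footnote gives the number of composites that contain a filled component, by visit and study group.

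The replicate-substitution and Day 1 carry-forward rules can stay as they are.

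The cost is a few sentences and one flag in the analysis dataset; the composite results do not change. The downside is that n in a component table may be slightly smaller than in the composite table, and component mean changes need not sum exactly to the composite mean change. A table note can say so.

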3.2. General Methods

As this is an extension study, formal statistical hypothesis testing will not be performed. All summaries are descriptive.

All data will be presented in by-patient data listings. The listings that contain an evaluation date will include 2 study days as described below:

- 1) Extension study day: the study day relative to the first dose date of patisiran in this study. The first dose date is designated as Day 1. On-treatment study days will be calculated as evaluation date – first dose date +1 and pre-treatment days will be calculated as evaluation date – first dose date. For example, the day prior to the first dose of patisiran will be Day -1 and the day after the first dose of patisiran will be Day 2, etc.
- 2) Parent study day: the study day relative to the day of the first dose of study drug in the parent study (Study 004 or 003).

All output will be incorporated into Microsoft Word files, sorted and labeled according to the International Conference on Harmonisation (ICH) recommendations, and formatted to the appropriate page size(s).

For categorical variables, summary tabulations of the number and percentage of patients within each category (with a category for missing data) of the parameter will be presented. For continuous variables, the number of patients, mean, median, standard deviation (SD), minimum, and maximum values will be presented.

Laboratory data (including vitamin A) collected and recorded as below the limit of detection will be set equal to the lower limit of detection for the calculation of summary statistics.

For assessments with planned repeat assessments at a given study visit (e.g., 10-meter walk tests), the average will be calculated unless otherwise noted.

All data recorded on the eCRF will be included in data listings.

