3.4. Baseline Definitions

Unless noted otherwise, baseline will be defined as the last non-missing measurement on or prior to the first dose of patisiran in this study. For several procedures, the last testing visit in the parent study will serve as the baseline for this study, unless more than 45 days have elapsed, in which case the test will need to be repeated on Day 1 in this study; see Table 1 of the study

protocol for additional details. If more than 45 days have elapsed and the assessment is not repeated on Day 1, the last assessment from the parent study will serve as baseline for this study; any such occurrence will be identified as a protocol deviation.

For the mNIS+7/NIS+7 individual components, total scores and related endpoints, grip strength test, and 10-meter walk test, baseline will be calculated as the average of 2 replicates.

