4.2. Demographics and Baseline Characteristics

Demographic and baseline characteristics, baseline disease characteristics, baseline efficacy parameters, and medical history information will be summarized by study group and overall. No formal statistical comparisons will be performed.

Age, height, weight, and body mass index (BMI) will be summarized using descriptive statistics (number of patients, mean, SD, median, minimum, and maximum). Sex, race, ethnicity, and region will be summarized by presenting the numbers and percentages of patients in each category.

The following baseline disease characteristics will be summarized by presenting the numbers and percentages of patients in each category:

- Genotype (V30M vs non-V30M)
- Karnofsky Performance Status (KPS)
- Concurrent Stabilizer Use at Study Entry (yes, no)

Concurrent stabilizer use at study entry is defined as patients who were receiving TTR tetramer stabilizers (tafamidis or diflunisal) for at least 2 weeks within the first month following the first dose of patisiran in Study 006.

Time in years since diagnosis with hATTR will be summarized using descriptive statistics.

Baseline values of continuous efficacy parameters (mNIS+7, Norfolk QOL, NIS-W, mBMI, 10-meter walk test, COMPASS-31, NIS, NIS+7, grip strength, EQ-5D-5L, EQ-VAS, R-ODS, IENFD distal thigh and distal leg, and SGNFD distal thigh and distal leg) will be summarized using descriptive summary statistics. The numbers and percentages of patients in each category for baseline PND score (I, II, IIIA, IIIB, IV), baseline FAP stage (0, I, II, III), and baseline NYHA class (I, II, III, IV) will also be summarized.

All demographic and baseline data for each patient will be provided in data listings.

Medical history will be summarized by MedDRA system organ class (SOC), high level term (HLT) and preferred term (PT). A patient contributes only once to the count for a given condition (overall, by SOC, by HLT, by PT). Medical history including prior surgeries and pregnancy test results will be presented in data listings.

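### Under the SAP's no-imputation default, patients who cannot complete the 10-meter walk leave the walk-speed summaries, unless data capture already records a speed of 0

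*SAP*

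**What the plan says.** SAP Section 4.5 makes walking a timed test: "Motor function assessments will include a timed 10-meter walk test and test of grip strength in the dominant arm". The planned output is descriptive: "The observed values and changes from baseline in 10-meter walk test speed and grip strength will be summarized". It is produced on the full analysis set at each scheduled time point, by study group and overall.

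Section 3.10.1 names the instruments that have missing-data algorithms: "mNIS+7, NIS+7, Norfolk QOL-DN, EQ-5D-5L, R-ODS, and COMPASS-31; see Section 7.1, Section 7.2, Section 7.3, Section 7.4, and Section 7.5". For the rest it says: "In general, there will be no imputation for missing data for other efficacy endpoints unless specified otherwise".

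Only two other rules touch the walk test, and both concern replicates:
- Section 3.2: "For assessments with planned repeat assessments at a given study visit (e.g., 10-meter walk tests), the average will be calculated unless otherwise noted".
- Section 3.4: "grip strength test, and 10-meter walk test, baseline will be calculated as the average of 2 replicates".

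Section 7 has no walk-test entry. On ambulation more broadly, Section 4.5 adds: "Categorical summaries of FAP stage and PND score will also be provided". Section 4.2 lists baseline categories up to PND IV and FAP III.

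**The concern.** Speed is distance over time. A patient who cannot cover the 10 meters has no time, and under the default no value is put in its place. The patient then contributes neither a speed nor a change at that visit. The value is absent because the outcome is the worst the test can give, so the patients who remain in the table are selected on the outcome itself.

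Elsewhere the SAP gives inability a score at the bad end of the scale. R-ODS scores 0 for an activity the patient cannot do (Section 7.4), and NIS-W scores 4 for paralysis (Section 7.1.1.1). Walking has no such rule, although speed has a natural floor of 0.

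All summaries are descriptive, so no model or sensitivity analysis would reveal the selection. Section 3.2 gives a missing category to categorical variables only. A continuous table shows the number of patients, but not how many are absent because they could not walk. Interim summaries are planned for regulatory use and publication (Section 3.12), so the rule should be settled before they are run.

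**Working it through.** **Is there an exception?** The relevant rules, side by side:

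| SAP section | Rule | Covers inability to walk? |
|---|---|---|
| 3.10.1 | Algorithms for six instruments; no imputation otherwise | Walk test not among the six |
| 3.2 | Repeats at a visit are averaged | No |
| 3.4 | Baseline is the mean of two replicates | No |
| 4.5 | Summarize speed and its change | No |
| 7 | Scoring appendices | No walk-test entry |

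Nothing in the SAP overrides the default. Exclusion follows unless the recorded value is already 0.

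**Direction and size.** The SAP gives no walk speeds, no rate of loss of walking and no sample-size calculation, so there is no figure of its own to reproduce. Every input below is an assumption:
- p: share who walk at baseline and cannot at the visit, 2% to 15%
- q: share who cannot walk at baseline and can at the visit
- bL: baseline speed of those who lose walking, 0.2 to 0.5 m/s
- g: speed of those who regain walking
- dW: mean change among patients who walk at both times, -0.05 to +0.05 m/s
- u: share unable to walk at the visit, 2% to 15%
- mW: mean speed of those still walking, 0.6 to 1.0 m/s

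*Mean speed at a visit.* The walkers-only mean is mW. With inability counted as 0 it is (1 − u) × mW. The difference is u × mW, which is never negative.
- u = 5%, mW = 0.8: 0.95 × 0.8 = 0.76, against 0.80.
- u = 10%, mW = 0.8: 0.90 × 0.8 = 0.72, against 0.80.
- Over the assumed ranges: 0.02 × 0.6 = 0.012 to 0.15 × 1.0 = 0.15 m/s.

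*Mean change, nobody regaining.* The walkers-only mean is dW. With inability counted as 0 it is (1 − p) × dW − p × bL. The difference is p × (dW + bL). It is positive, that is, toward benefit, whenever dW > −bL.
- p = 5%, bL = 0.4, dW = 0: 0.05 × 0.4 = 0.02 m/s.
- p = 10%, bL = 0.5, dW = 0: 0.10 × 0.5 = 0.05 m/s.
- p = 10%, bL = 0.5, dW = +0.05: +0.050 reported, against 0.90 × 0.05 − 0.10 × 0.5 = −0.005. The sign changes.
- Over the assumed ranges: 0.02 × (−0.05 + 0.2) = 0.003 to 0.15 × (0.05 + 0.5) = 0.0825 m/s.

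*Mean change, some regaining.* A patient with no baseline speed also has no change score. The net difference becomes p × (dW + bL) − q × (g − dW). With bL = g = 0.3 and dW = 0:

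| p | q | Net shift (m/s) |
|---|---|---|
| 5% | 0% | 0.05 × 0.3 = +0.015 |
| 5% | 2% | 0.015 − 0.02 × 0.3 = +0.009 |
| 5% | 5% | 0.015 − 0.05 × 0.3 = 0 |
| 2% | 5% | 0.006 − 0.015 = −0.009 |

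The shift in mean speed has one direction. The shift in mean change depends on the balance of loss and recovery.

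**The case against.** The strongest reply is that the SAP never says non-walkers are excluded. Section 3.10.1 deals with missing data, and a patient assessed and found unable to walk arguably has an observed result. The endpoint is a speed, which can take 0 without imputation, and the protocol or eCRF may record it so. This stands as a condition on the finding: if 0 is already entered, the results do not change. It does not remove the need for the rule, because the SAP as written leaves the walk test under the default.

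Second, loss of walking is visible elsewhere. PND and FAP are tabulated by time point and group, continuous tables show the number of patients, and non-walkers can still contribute to NIS-W and R-ODS. This limits the harm. It does not correct the mean speed or its change.

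Third, walk speed is one of more than a dozen descriptive assessments, with no hypothesis test attached. This stands. A reader might take change in walk speed to be the study's efficacy answer, but the SAP gives it no such rank.

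Fourth, zeros mix walkers and non-walkers in one mean. That is a real cost, met by also showing the walkers-only summary.

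A reader might carry the point over to grip strength. Nothing in the SAP suggests that inability to grip gives a missing value rather than a reading of zero. A reader might also take the PND and FAP categories as a forecast that patients will lose walking on study. Section 4.2 lists baseline categories and does not define them.

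**Conclusion.** The point holds, on condition that inability to walk is not already captured as 0. Under the stated default, patients unable to complete the walk because of disease leave both walk-speed summaries, and their absence is informative. Mean speed is then too high whenever anyone is unable to walk. Mean change shifts toward benefit when more patients lose walking than regain it, for similar speeds and little change in the rest.

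A reader might infer that the plan is shown to be biased toward benefit. The documents do not support that: recovery of walking offsets the shift in mean change and can reverse it. Nor do they support a claim that the prior-treatment groups are affected unequally, since no rates of lost walking are given for them.

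The size cannot be derived from the documents. The 0.02 m/s illustration rests on an assumed 5% loss, an assumed 0.4 m/s baseline speed, no change in the others and no recovery. The analysis is descriptive, so this is a change that should be made, not one on which a formal conclusion depends.

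**What to change.** Add to Section 3.10.1 or 4.5 of the SAP: a patient unable to perform the 10-meter walk because of disease is assigned a speed of 0 m/s at that visit, including at baseline; walks missed for any other reason remain missing. Report the number set to 0 by visit and study group, and keep the walkers-only summary as a supplement. Applying the rule at baseline also counts patients who regain walking, so the correction is not one-sided. If the data capture already records 0, one sentence saying so is enough, with the counts.

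The cost is a short addition to the text and a derivation. The reason for each missed walk must be available. The main mean will then combine walkers and non-walkers, which is why the counts and the supplement should appear beside it.
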